4.4.2 Dose Increase / Dose Reduction

As per the package insert,³ increments in AUSTEDO dosing will be done by 6 mg/week up to a maximum of 48 mg/day. Study subjects who are unable to tolerate this dose will be allowed to remain on the maximum well-tolerated dose of AUSTEDO. If this dose has not been previously established, they will be instructed to reduce the total daily AUSTEDO dose by 6 mg (1 tablet) every day until the maximum well-tolerated dose of AUSTEDO is established. A faster dose reduction will be allowed if deemed necessary by the investigator. In study subjects receiving a strong CYP2D6 inhibitor, the maximum allowed dose of AUSTEDO will be 36 mg/day.

Patients will be contacted on a weekly basis via telephone during the ramp-up period to assess study drug tolerability. Dose reductions will be allowed in this period at the discretion of the investigator, but also during the maintenance period. A dose reduction during the ramp-up period will determine the start of the maintenance period, as it will be assumed that the new, lower AUSTEDO dose is the maximum well-tolerated dose of AUSTEDO for that study subject. Similarly, subjects will remain on the new, maximum well-tolerated dose of AUSTEDO for the remainder of the trial once a dose reduction is done during the maintenance period.

4.5 Study Drug Accountability

All study drug supplied is for use only in this clinical study and will not be used for any other purpose. The Investigator is responsible for the study drug accountability, reconciliation and record maintenance at the investigational site. In accordance with all applicable regulatory requirements, the Investigator or designated site staff will maintain study drug accountability records throughout the course of the study.

This person will document the amount of study drug received and the amount supplied and/or administered to and returned by subjects, if applicable. Copies of all packing slips for the study drug shipments will be retained.

A Study Drug Accountability Record will be kept current and will contain at a minimum the following information:

- The identification of the subject to whom the drug was dispensed
- The date(s) and quantity of the drug dispensed to the subject
- Any product accidentally or deliberately destroyed
- Current quantity of total study drug supply

Subjects will be instructed to return all used and unused bottles (with unused capsules) of study drug for drug accountability purposes. All used and unused bottles (with unused capsules) will be saved for reconciliation by the Sponsor's study monitor or an assigned designee. During the study, the study drug and all shipment, accountability and dispensing records will be available for inspection by the study monitor. Drug supply reconciliation is required at the end of the study.

4.6 Study Drug Handling and Disposal

After reconciliation, unused or partially used study drug may be destroyed by the Investigator only after authorization from Teva, and according to instructions provided by Teva, provided such disposition does not expose humans to risk from the drug. The Investigator or their designee will maintain records of any such alternative disposition of the study drug. These records will show the identification and quantity of each unit that has been disposed, the method of destruction, and the person who disposed of the study drug. Alternatively, the Investigator may elect to return unused or partially used drug supplies to Teva, or the sponsor's designee, instead of destroying them on-site.

4.7 Prohibited Medications and Restrictions

Reserpine

Reserpine is an irreversible VMAT2 inhibitor, and, thus, will not be used concomitantly with AUSTEDO. In clinical practice, at least twenty (20) days must elapse after stopping reserpine before starting AUSTEDO.

Monoamine Oxidase Inhibitors

AUSTEDO is contraindicated in subjects taking MAOIs. In clinical practice, AUSTEDO will not be used in combination with an MAOI, or within 14 days of discontinuing therapy with an MAOI.

Tetrabenazine

AUSTEDO is contraindicated in subjects currently taking tetrabenazine. In clinical practice, AUSTEDO may be initiated the day following discontinuation of Tetrabenazine.

AUSTEDO is also contraindicated in subjects:

- Who are suicidal, or in subjects with untreated or inadequately treated depression.
- With hepatic impairment.
- 4.8 Concomitant Medications

Strong CYP2D6 inhibitors

As per the package insert,³ concomitant use of strong CYP2D6 inhibitors has been shown to increase the systemic exposure to the active dihydro-metabolites of AUSTEDO by approximately 3 fold. The daily dose of AUSTEDO will not exceed 36 mg per day, and the maximum single dose of AUSTEDO will not exceed 18 mg in subjects taking these inhibitors.

Table 5 below shows a list of strong CYP2D6 inhibitors:

Table 5 Strong CYP2D6 inhibitors
Bupropion
Fluoxetine
Paroxetine
Quinidine
Terbinafine

Neuroleptics

The risk for parkinsonism, NMS, and akathisia may be increased by concomitant use of AUSTEDO and dopamine antagonists or antipsychotics. As per the inclusion/exclusion criteria, subjects with a history of psychiatric disease or taking an antipsychotic (even if for a non-psychiatric reason) are not eligible for participation in the AUDYT trial.

Alcohol or other sedatives

Concomitant use of alcohol or other sedating drugs may have additive effects and worsen sedation and somnolence. As mentioned in the exclusion criteria, no change in the dose of psychoactive medications will be allowed for the duration of the trial, or at least 30 days prior to screening. Subjects will be encouraged to abstain from alcohol for the duration of the trial.

Drugs causing QTc prolongation

Table 6 below shows a list of medications that are known to prolong the QTc. Subjects taking these medication will be allowed to participate in the trial as long as their ECG during visit 1 (and while already on one or more of these drugs at steady state) shows no QTc prolongation. Any evidence of QTc prolongation during subsequent ECGs will require an adjustment in the AUSTEDO dose as detailed elsewhere. The introduction of these medications will not be allowed for the duration of the trial. If it is determined that a subject requires one of these medications during their participation in the trial, AUSTEDO will be stopped and the subject will be considered withdrawn from the trial.

Table 6 Drugs causing QTc prolongation
Moxifloxacin
Quinidine
Procainamide
Amiodarone
Sotalol

4.9 Overdose

According to the package insert,³ overdoses ranging from 100 mg to 1 g have been reported in the literature with tetrabenazine, a closely related VMAT2 inhibitor. The following adverse reactions occurred with overdosing: acute dystonia, oculogyric crisis, nausea and vomiting, sweating, sedation, hypotension, confusion, diarrhea, hallucinations, rubor, and tremor.

All overdoses will be reported to the sponsor. Minor overdoses will be managed according to the sponsor's guidelines. However, suicide attempts, should they happen, will be managed in the same way as attempts by non-study subjects: 911 will be called to guarantee prompt access to the nearest medical facility. As with the management of overdosage with any central nervous system-active drug, general supportive and symptomatic measures will be recommended. Cardiac rhythm and vital signs should be monitored. In managing overdosage, the possibility of multiple drug involvement should be considered. The treating physician during hospitalization will consider contacting a poison control center on the treatment of any overdose. Telephone numbers for certified poison control centers are listed on the American Association of Poison Control Centers website www.aapcc.org.

4.10 Treatment Compliance

During Visit 1, the total number of tablets that each study subject will need for the duration of the trial will be dispensed. Compliance will be assessed during Visit 5, that is, during the 1-week post-treatment Visit. The number of returned tablets will be counted by the Investigator, or a designee, and recorded in the Drug Dispensing Log. At least 80% compliance will be defined as acceptable in this study. Compliance with study drug intake will be assessed verbally (subject's report, no tablet counting) and encouraged during all other study Visits.

- 5. ADVERSE EVENTS
- 5.1 Definitions
- 5.1.1 Adverse Event Definitions

During the study, the Investigator or study site personnel will be responsible for querying and recording adverse events (AEs) and serious adverse events (SAEs), as detailed in this section of the protocol. This includes the weekly communications with the study subjects via telephone during the ramp-up period. In this study AEs and SAEs will be reported from the time of study drug administration until the last study Visit or death, whichever occurs first.

An adverse event (AE) is any untoward medical occurrence that occurs in conjunction with the use of a medicinal product in humans, whether or not considered to have a causal relationship to the medicinal product. An AE can, therefore, be any unfavorable or unintended sign (including a clinically significant abnormal laboratory finding), symptom, or disease temporally associated with the use of a medicinal product, whether or not it is a direct consequence of study drug use.

Any medical condition or clinically significant laboratory abnormality with an onset date before the first date of study drug administration will be considered to be pre-existing, and will not be recorded as an AE. Any AE (i.e., a new event or an exacerbation of a pre-existing condition) with an onset date after study drug administration up to and including the designated follow-up safety Visit will be recorded as an AE. All AEs will be recorded regardless of the severity or relationship to study medication. All AEs that result in permanent discontinuation of the study drug being studied, whether serious or nonserious, will be reported.

An AE does include:

- an exacerbation of a pre-existing illness
- an increase in frequency or intensity of a pre-existing episodic event or condition
- a condition detected or diagnosed after study drug administration even though it may have been present prior to the start of the study
- persistent disease or symptoms present at baseline which worsen following the start of the study

An AE does not include:

- medical or surgical procedures (e.g., surgery, endoscopy, tooth extraction, transfusion) Note: in this case, the condition that led to the procedure is an AE
- pre-existing diseases or conditions present or detected prior to start of study drug administration, which do not worsen
- the disease or disorder being studied or a sign or symptom associated with that disease (i.e., signs or symptoms associated with lack of efficacy will generally be considered to reflect underlying disease, rather than AEs)
- situations where an untoward medical occurrence has not occurred (e.g., hospitalization for elective surgery, social, and/or convenience admissions)
- overdose of either study drug or concomitant medication without any signs or symptoms

All AEs will be fully and completely recorded. The following attributes will be assigned: description of AE, dates and times of onset and resolution (or whether ongoing), severity, causality to study drug, whether an SAE or not, and action taken (i.e., no action taken; study medication interrupted; study medication discontinued; other).

In the event that a subject is withdrawn from the study because of an AE, it will be recorded. The subject will be followed and treated by the investigator until the AE has resolved or a new chronic baseline has been established. The investigator will report all directly observed AEs and all spontaneously reported AEs. At each Visit the investigator will ask the subject a nonspecific question (e.g., "Have you noticed anything different since your last Visit?") to assess whether any AEs have occurred since the last report or Visit. AEs will be identified and recorded in appropriate medical terminology.

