LOWER FACE (including platysma)					
JAW & TONGUE					
LARYNX (including pharynx)					
NECK					
SHOULDER & PROXIMAL ARM		R	L		
ELBOW, DISTAL ARM, HAND		R	L		
PELVIS & UPPER LEG		R	L		
DISTAL LEG & FOOT		R	L		
TRUNK					
TOTAL SCORE (Sum of all body parts)					

Rate the patient according to body part indicated from 1-10, in relationship to all patients. A score of 0 is no dystonia in that body area. A score of 5 is moderate dystonia. A score of 10 is the most severe dystonia encountered. If the dystonia changes during the examination, rate the maximal dystonia. For mixed motor syndromes, rate only dystonia and not the other components.

- 3.7 Study Endpoints
- 3.7.1 Safety Endpoints
- 3.7.1.1 Primary Safety Endpoint

The primary safety endpoint for the AUDYT trial will be the proportion of study subjects able to titrate up to 48 mg/d (or up to 36 mg/d if receiving a strong CYP2D6 inhibitor) and able to complete the study at this dosage. The reason(s) why subjects are unable to titrate or maintain the maximal recommended AUSTEDO dose will be recorded and reported, when appropriate.

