4.3 Study Drug Storage

As per the package insert,³ AUSTEDO will be stored at 25° C (77°F); excursions permitted to 15°C to 30°C (59°F to 86°F). It will be protected from light and moisture.

- 4.4 Administration
- 4.4.1 Route of Administration and Dose Schedule

According to the package insert,³ the dose of AUSTEDO is determined individually for each patient with Huntington's Disease based on reduction of chorea and tolerability. When first prescribed to subjects who are not being switched from tetrabenazine (a related VMAT2 inhibitor), the recommended starting dose of AUSTEDO is 6 mg administered orally once daily. The dose of AUSTEDO may be increased at weekly intervals in increments of 6 mg per day to a maximum recommended daily dosage of 48 mg. Total daily dosages of 12 mg or above will be administered in two divided doses. AUSTEDO will be administered with food. AUSTEDO will be swallowed whole. It will not be chewed, crushed or broken.

Based on these recommendations (and as shown in Table 3 below), for the purpose of the AUDYT trial, each study subject is expected to start, increase, maintain and then discontinue AUSTEDO 6 mg tablets as follows:

Table 3
Expected study drug titration for subjects able to increase AUSTEDO to 48 mg/day

				Total	Total
		Number of		number of	number of
	Number of	afternoon	Total daily	tablets per	tablets per
	morning tablets	tablets	dose (mg)	day	week
Week 1	1	1	12	2	14
Week 2	1	2	18	3	21
Week 3	2	2	24	4	28
Week 4	2	3	30	5	35
Week 5	3	3	36	6	42
Week 6	3	4	42	7	49
Week 7	4	4	48	8	56
Week 8	4	4	48	8	56
Week 9	4	4	48	8	56
Week 10	4	4	48	8	56
Week 11	4	4	48	8	56
Week 12	4	4	48	8	56
Week 13	0	0	0	0	0

Table 4 below shows how subjects receiving a strong CYP2D6 inhibitor will start, increase, maintain and then discontinue AUSTEDO 6 mg tablets:

Table 4
Expected study drug titration for subjects able to increase AUSTEDO to 36 mg/day

				Total	Total
		Number of		number of	number of
	Number of	afternoon	Total daily	tablets per	tablets per
	morning tablets	tablets	dose (mg)	day	week
Week 1	1	1	12	2	14
Week 2	1	2	18	3	21
Week 3	2	2	24	4	28
Week 4	2	3	30	5	35
Week 5	3	3	36	6	42
Week 6	3	3	36	6	42
Week 7	3	3	36	6	42
Week 8	3	3	36	6	42
Week 9	3	3	36	6	42
Week 10	3	3	36	6	42
Week 11	0	0	0	0	0

In subjects receiving a strong CYP2D6 inhibitor, the ramp-up period will be reduced to 4 weeks, reducing the duration of their participation in the study to 11 weeks.

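### Completion at the full dose rests on self-report, and the single pooled tablet count cannot separate 48 from 36 mg/day in maintenance

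*Combined protocol and SAP*

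**What the plan says.** Section 3.7.1.1 defines the primary safety endpoint as the proportion of subjects able to titrate to 48 mg/day, or 36 mg/day with a strong CYP2D6 inhibitor, "and able to complete the study at this dosage". It adds: "The reason(s) why subjects are unable to titrate or maintain the maximal recommended AUSTEDO dose will be recorded and reported, when appropriate". Section 3.1 says that dose reductions due to adverse events are recorded.

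Section 4.10 sets out how intake is checked. At Visit 1, "the total number of tablets that each study subject will need for the duration of the trial will be dispensed". Then: "Compliance will be assessed during Visit 5, that is, during the 1-week post-treatment Visit". For the rest: "Compliance with study drug intake will be assessed verbally (subject's report, no tablet counting) and encouraged during all other study Visits". The standard is: "At least 80% compliance will be defined as acceptable in this study". No denominator, period or formula is given, and nothing links this standard to the primary endpoint. The Visit 5 activity list and Appendix 1 agree with section 4.10: bottles come back at Visit 5, or at an Early Termination Visit, and not before.

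Weekly telephone calls are described for the ramp-up period only (sections 3.1, 3.5.1.2 and 4.4.2). On the 48 mg/day schedule, Visit 3 falls in week 7 and Visit 4 in week 12 (sections 3.5.1.3 and 3.5.1.4). Planned tablets per week are in Tables 3 and 4 of section 4.4.1; Table 3 is headed "Expected study drug titration for subjects able to increase AUSTEDO to 48 mg/day".

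**The concern.** The endpoint turns on the dose actually taken in the six maintenance weeks. In that period the plan has no objective measure of intake. The calls have ended, no contact is scheduled between Visits 3 and 4, and at both visits intake is what the subject says it is. The Visit 5 count is objective, but it gives one total for ramp-up and maintenance together, so missed tablets cannot be placed in either period. Intake in ramp-up also dilutes a shortfall in maintenance when the total is compared with 80%.

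A subject who takes less than the full dose because of side effects, and does not say so, could therefore be counted as having tolerated it. That error would raise the tolerability proportion. The study is meant to support larger trials, so an inflated figure would carry forward. It could not be corrected afterwards, because without a count near the start of maintenance the two periods cannot be separated.

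**Working it through.** **Inputs.** Tablets are 6 mg (section 1.3.1). Weekly tablet numbers come from Tables 3 and 4. Maintenance is 6 weeks, or 42 days (section 3.4.3). The threshold is 80% (section 4.10). The planned number of subjects is 15 (section 3.3). *Assumption:* compliance = tablets taken / tablets planned over the whole study.

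**Reproducing Table 3.** Morning plus afternoon tablets, times 6 mg, gives the daily dose; times 7, it gives tablets per week. All 12 dosing rows agree with the table.
- Ramp-up: 14 + 21 + 28 + 35 + 42 + 49 = 189
- Maintenance: 6 × 56 = 336
- Total: 189 + 336 = 525; 80% of 525 = 420

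**Full ramp-up, then a lower average in maintenance (48 mg/day schedule).**

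| Average taken in maintenance | Tablets in 42 days | Share of 525 | Share of 336 |
|---|---|---|---|
| 48 mg/day | 336 | 100% | 100% |
| 42 mg/day | 294 | 483/525 = 92.0% | 87.5% |
| 36 mg/day | 252 | 441/525 = 84.0% | 75.0% |
| 30 mg/day | 210 | 399/525 = 76.0% | 62.5% |

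Lowest passing average: (420 − 189)/42 = 5.5 tablets/day, and 5.5 × 6 = 33 mg/day.

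**Why one count cannot settle it.** At 36 mg/day in maintenance, 336 − 252 = 84 tablets come back. The same 84 come back from a subject who took 189 − 84 = 105 tablets in ramp-up and all 336 in maintenance.

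**Table 4 (36 mg/day schedule).** Ramp-up is 14 + 21 + 28 + 35 = 98, maintenance 6 × 42 = 252, total 350, and 80% is 280. An average of 30 mg/day in maintenance gives (98 + 210)/350 = 88.0%; 24 mg/day gives (98 + 168)/350 = 76.0%. Lowest passing average: (280 − 98)/42 × 6 = 26 mg/day.

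**Sensitivity to the denominator.** If supply is reckoned in whole 60-tablet bottles (assumption: 9 bottles, 540 tablets), 36 mg/day gives 441/540 = 81.7%, which still passes. The lowest passing average becomes (432 − 189)/42 × 6 = 34.7 mg/day.

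**The 80% rule on maintenance alone.** 0.80 × 48 = 38.4 mg/day, so 36 mg/day (75%) is flagged. An average of 42 mg/day (87.5%) is not, nor is 30 of 36 mg/day (83.3%) on the other schedule.

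**Weight of one subject.** 1/15 = 6.7 percentage points, if all 15 enter the analysis.

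**The case against.** The strongest reply is that the plan already catches most of this. Reductions for adverse events are recorded, as are reasons for not holding the maximal dose. Adverse events are asked about at every visit and in the ramp-up calls. The trial is open-label, and subjects may step down and stay in, so they have little reason to hide a reduction. This stands: it confines the problem to under-dosing that is not disclosed, and nothing in the documents says how common that would be. Forgetting is as possible a cause as poor tolerability.

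A reader might infer that 80% compliance makes a subject a success. The documents do not say so. No section ties the 80% standard to the endpoint, and a subject known to be on 36 mg/day without a strong CYP2D6 inhibitor does not meet its wording. A reader might also infer that the efficacy objectives carry the same error. They do not, because section 2.2 sets them at 48 mg daily or the highest tolerated dose.

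Two further replies have force. The Visit 5 count would show 84 surplus tablets even where 80% is met; this is true, but it cannot say when they were missed. And building an adherence cut into an endpoint about being able to complete at a dose would turn a subject who merely forgets tablets into a tolerability failure. That is a good reason to leave the definition alone and put intake beside it.

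The last reply, that this is a 15-subject pilot not powered for efficacy, does not remove the point, because tolerability is what the pilot is for.

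**Conclusion.** The concern holds in a limited form. Completion at the full dose is verified in maintenance only by self-report, and the single count pools that period with ramp-up. On the assumed whole-study denominator, undisclosed intake averaging 36 mg/day throughout maintenance reads as 84.0% and acceptable, though it is 75% of the maintenance tablets. The passing floor is 33 mg/day on the Table 3 schedule and 26 mg/day on Table 4. The 36 mg/day result also survives the bottle-based denominator.

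The figure of 6.7 points is the size of one misclassification. It is not evidence that any will occur, and the documents do not support a claim that the primary result is biased by a known amount. This is a measurement point and implies no view on any dose. It should be acted on because the remedy is cheap and the split between the two periods cannot be recovered later.

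**What to change.** In section 4.10, have subjects bring their bottles to Visit 3 and count the tablets there. Visit 3 falls within the first maintenance week, not necessarily on its first day, so adjust for the date: tablets counted at Visit 3 minus tablets returned at Visit 5, divided by the prescribed tablets per day times the days from Visit 3 to the last dose. State the compliance denominator, including how a directed reduction changes it, and apply the 80% rule to maintenance separately.

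Keep the definition in section 3.7.1.1. Report next to the proportion:
- the mean daily dose taken in maintenance, which also shows shortfalls that an 80% cut lets through, such as 42 of 48 mg/day;
- as a sensitivity analysis, the proportion who meet the endpoint and also took at least 80% of their maintenance tablets, with the denominator unchanged.

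The cost is one extra count per subject at a visit already scheduled, with matching edits to the Visit 3 list and Appendix 1, and a few sentences of text. The sensitivity figure may be lower than the primary one.
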